7.22 Definitions of DLT

7.221 For this protocol, dose-limiting toxicity (DLT) will be defined as an adverse event at least possibly related to treatment (definitely, probably, or possibly related) that occurs in cycle 2 of the study treatment and meets the following criteria:

| Toxicity | DLT Definition |
|-----------------|--|
| Hematologic | ANC $\leq 0.5 \times 10^{9}$ /L for more than 14 |
| - | days |
| | Febrile neutropenia of any duration |
| | $(ANC < 1.0 \text{ x } 10^{9}/\text{L}, \text{ fever} \ge 38.5^{\circ}\text{C})$ |
| | Grade 4 thrombocytopenia or Grade |
| | 3 thrombocytopenia with bleeding or |
| | any requirement for platelet |
| | transfusion |
| | Grade 4 anemia, unexplained by |
| | underlying disease |
| Non-hematologic | Any grade 3 or 4 (except tumor lysis |
| | syndrome, tumor flare reaction, |
| | fatigue, nausea, hyperglycemia in |
| | diabetic patients) |

| Dose Level | Lenalidomide | AT-101 |
|---------------|--------------|--------------|
| -2 | 5 mg | 20 mg b.i.d. |
| -1 | 5 mg | 30 mg b.i.d. |
| 1* | 5 mg | 40 mg b.i.d. |
| 2 | 10 mg | 40 mg b.i.d. |
| 3 | 15 mg | 40 mg b.i.d. |
| 4 | 20 mg | 40 mg b.i.d. |

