| Cardiac Disorders | Sinus bradycardia/ other cardiac Arrhythmia Grade 2 | | Omit dose. Follow at least weekly. If the toxicity resolves to ≤ grade 1, reduce dose by one dose level (5mg) and continue therapy. | |
| | \geq Grade 3 | | • Discontinue study treatment and go to | |
| Vascular disorders | thromboembolic event \geq Grade 3 | | event monitoring. Omit dose and start anticoagulation; restart at investigator's discretion (maintain dose level). | |

| \rightarrow \rightarrow Use the NCI Common Terminology Criteria for Adverse Events (CTCAE) version 4.0 unless | | | |
|---|--|--------------------------|--|
| | otherwise | e specified \leftarrow | F |
| CTCAE System/Organ/Class (SOC) | ADVERSE EVENT | AGENT | ACTION |
| | BASED ON INTERVAL | ADVERSE E | VENTS (Days 2-28) |
| Immune system disorders | Allergic reaction Grade 2-3 | | Omit dose. Follow at least weekly. If the toxicity resolves to ≤ grade 1, reduce dose by 5 mg and continue therapy. |
| Anaphylaxis Grade 4 | | | • Discontinue study treatment and go to event monitoring. |
| | Erythema multiforme ≥ Grade 3 | Г | • Discontinue study treatment and go to event monitoring. |
| Skin and | Skin ulceration \geq Grade 2 | Lenalidomide | • Discontinue study treatment and go to event monitoring. |
| subcutaneous tissue disorders | Other: Non-blistering rash Grade 3 | | If Grade 3 omit dose. Follow weekly. If the toxicity resolves to ≤ grade 2 continue therapy. |
| | Other: Non-blistering rash Grade 4 | | • Discontinue study treatment and go to event monitoring. |
| Other | Non-hematologic toxicity assessed as lenalidomide related ≥ Grade 3 | | Omit dose. Follow at least weekly. If the toxicity resolves to ≤ grade 2, implement one dose reduction step and continue therapy. |

* use IWCLL/Hallek, December 2008 criteria (see Appendix V)

NOTE: Subjects who cannot tolerate the minimum dose 5 mg daily on days 1 - 21 of a 28 day cycle, are to be discontinued from the treatment phase of the study and go to event monitoring.

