10.0 Adverse Event (AE) Reporting and Monitoring

10.1 Adverse Event Characteristics

CTCAE term (AE description) and grade: The descriptions and grading scales found in the revised NCI Common Terminology Criteria for Adverse Events (CTCAE) version 4.0 will be utilized for AE reporting. All appropriate treatment areas should have access to a copy of the CTCAE version 4.0. A copy of the CTCAE version 4.0 can be downloaded from the CTEP web: (http://ctep.cancer.gov/protocolDevelopment/electronic applications/ctc.htm)

10.11 Adverse event monitoring and reporting is a routine part of every clinical trial. First, identify and grade the severity of the event using the CTCAE version 4.0. Next, determine whether the event is expected or unexpected (see Section 10.2) and if the adverse event is related to the medical treatment or procedure (see

Section 10.5). With this information, determine whether the event must be reported as an expedited report (see Section 10.). Expedited reports are to be completed within the timeframes and via the mechanisms specified in Sections 10.4. All AEs reported via expedited mechanisms must also be reported via the routine data reporting mechanisms defined by the protocol (see Sections 10.6 and 18.0).

10.12 Each CTCAE term in the current version is a unique representation of a specific event used for medical documentation and scientific analysis and is a single MedDRA Lowest Level Term (LLT). Grade is an essential element of the Guidelines and, in general, relates to **severity** for the purposes of regulatory reporting to NCI.

NOTE: A severe AE, as defined by the above grading scale, is NOT the same as serious AE which is defined in the table in Section 10.4.

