10.41 Special Situations for Expedited Reporting and Submission of Notification Forms

Exceptions to Expedited Reporting and Submission of Notifcation Forms: EXPECTED Serious Adverse Events

An expedited report or notification form may not be required for specific Grade 1, 2 and 3 Serious Adverse Events where the AE is **EXPECTED**. Any protocol specific reporting procedures MUST BE SPECIFIED BELOW and will supercede the standard Expedited Adverse Event Reporting and Notification Form Requirements (Note: These adverse

| System Organ Class (SOC) | Adverse event/ Symptoms | CTCAE Grade at which the event will not be expeditedly reported ¹ . |
|--------------------------------------|----------------------------|--|
| Blood and lymphatic system disorders | Anemia | ≤4 |
| Investigations | White blood cell decreased | ≤ 4 |
| | Lymphocyte count decreased | ≤ 4 |
| | Neutrophil count decreased | ≤ 4 |
| | Platelet count decreased | < 4 |

events must still be reported through the routine reporting mechanisms [i.e. Nadir/adverse events form]; see footnote 1):

¹ These exceptions only apply if the adverse event does not result in hospitalization. If the adverse event results in hospitalization, then the standard expedited adverse events reporting requirments must be followed.

Specific protocol exceptions to expedited reporting should be reported expeditiously by investigators **ONLY** if they exceed the expected grade of the event.

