Pregnancies occurring while the subject is on study drug or within 4 weeks after the subject's last dose of study drug are considered immediately reportable events. If the subject is on study drug the study drug is to be discontinued immediately and the subject is to be instructed to return any unused portion of the study drug to the Investigator. The pregnancy must be reported to the Safety Monitor within 24 hours of the Investigator's knowledge of the pregnancy by phone and facsimile using the SAE Form.

Protocol Version Date: November 25, 2014

The Investigator will follow the subject until completion of the pregnancy, and must notify the Safety Monitor of the outcome within 5 days or as specified below. The Investigator will provide this information as a follow-up to the initial SAE.

If the outcome of the pregnancy meets the criteria for immediate classification as a SAE (i.e., spontaneous abortion [any congenital anomaly detected in an aborted fetus is to be documented], stillbirth, neonatal death, or congenital anomaly), the Investigator should follow the procedures for reporting SAEs (i.e., report the event to the Safety Monitor by telephone and facsimile within 24 hours of the Investigator's knowledge of the event).

All neonatal deaths that occur within 30 days of birth should be reported, without regard to causality, as SAEs. In addition, any infant death after 30 days that the Investigator suspects is related to the *in utero* exposure to the study drug should also be reported.

In the case of a live "normal" birth, the Safety Monitor should be advised as soon as the information is available.

10.6 **Required Routine Reporting**

Adverse events to be graded at each evaluation and pretreatment symptoms/conditions to be evaluated at baseline per the CTCAE v4.0 grading unless otherwise stated in the table below:

| System Organ Class (SOC) | Adverse event/Symptoms | Baseline | Each evaluation |
|--------------------------------------|---------------------------|----------|--------------------|
| Investigations | Platelet count decreased* | X | Х |
| Blood and lymphatic system disorders | Anemia* | X | Х |
| Gastrointestinal disorders | Constipation | Х | Х |
| | Ileus | | Х |

* Grading will be performed by the study statisticians at the time of analysis based on the CLL toxicity grading scale for blood counts in Appendix V. Anemia grade per CTCAE will also be recorded for reporting purposes.

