Appendix V Grading Scale for Hematologic Toxicity in CLL Studies

Non Hematologic Toxicity will be scored using NCI CTCAE (version 4.0) for toxicity and adverse event reporting.

Hematologic toxicity will be assessed using IWCLL/Hallek December 2008

Grading scale for hematologic toxicity in CLL studies

| Grade [*] | Decrease in platelets ¹ or Hb ⁺ (nadir) from pretreatment value, % | Absolute neutrophil count/µL ³ (nadir) |
|--------------------|--|--|
| 0 | No change to 10% | ≥ 2000 |
| 1 | 11%-24% | \geq 1500 and < 2000 |
| 2 | 25%-49% | $\geq 1000 \text{ and} < 1500$ |
| 3 | 50%-74% | \geq 500 and < 1000 |
| 4 | $\geq 75\%$ | < 500 |

^{*} Grades: 1, mild; 2, moderate; 3, severe; 4, life-threatening; 5, fatal. Death occurring as a result of toxicity at any level of decrease from pretreatment will be recorded as grade 5.

[†]Platelet counts must be below normal levels for grades 1 to 4. If, at any level of decrease, the platelet count is $< 20 \times 10^{9}/L$ (20 000/µL), this will be considered grade 4 toxicity, unless a severe or life-threatening decrease in the initial platelet count (eg, $20 \times 10^{9}/L$ [20 000/µL]) was present pretreatment, in which case the patient is not evaluable for toxicity referable to platelet counts.

[‡]Hb levels must be below normal levels for grades 1 to 4. Baseline and subsequent Hb determinations must be performed before any given transfusions. The use of erythropoietin is irrelevant for the grading of toxicity but should be documented.

[§]If the absolute neutrophil count (ANC) reaches $< 1 \ge 10^{9}$ /L (1000/µL), it should be judged to be grade 3 toxicity. Other decreases in the white blood cell count, or in circulating neutrophils, are not to be considered because a decrease in the white blood cell count is a desired therapeutic endpoint. A gradual decrease in granulocytes is not a reliable index in CLL for stepwise grading of toxicity. If the ANC was $< 1 \ge 10^{9}$ /L (1000/µL) before therapy, the patient is not evaluable for toxicity referable to the ANC. The use of growth factors such as G-CSF is not relevant to the grading of toxicity, but should be documented.

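### An ANC ≤0.5 episode starting on day 15 or later of cycle 2 cannot meet its 14-day DLT duration by day 28, and nothing holds the escalation decision; separately, the anemia limb is practically inert on Appendix V

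*Combined protocol and SAP*

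**What the plan says.** **Neutropenia limb and observation window.** A DLT under 7.221 is an at least possibly related event in cycle 2, the first cycle of the combination. One limb is an ANC at or below 0.5 × 10⁹/"L for more than 14" days. Under 7.212 the three patients of a cohort are watched to day 28 of the combination before new patients are treated. Under 16.222, if none of the three has a DLT, three new patients go to the next level. Section 16.221 asks for observation over two cycles as a minimum.

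**Blood counts.** Footnote 6 of the Test Schedule (4.0) leaves the cycle 2 day 8 and day 15 counts to the treating physician. The next scheduled count is the one before cycle 3.

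**Anemia and platelet limbs.** 7.221 lists "Grade 4 anemia, unexplained by" underlying disease. It also lists grade 4 thrombocytopenia, and grade 3 with bleeding or a platelet transfusion need. It names no scale for any of these. Two scales are in use elsewhere:

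- Appendix V: "Hematologic toxicity will be assessed using" the IWCLL/Hallek 2008 scale. Sections 16.231 and 16.232 apply it to platelets and hemoglobin in the phase I summaries.
- CTCAE, of which 10.1 says "version 4.0 will be utilized for AE reporting". Section 10.6 keeps both for anemia: "Grading will be performed by the study statisticians at the time of analysis based on the CLL toxicity grading scale", and "Anemia grade per CTCAE will also be recorded for reporting purposes".

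**The concern.** A duration criterion of more than 14 days sits inside a 28-day window, so it can be completed in time only by episodes that start in the first half of the cycle. A patient whose neutrophils fall in the third or fourth week has no neutropenia DLT at day 28, and as written the cohort moves on. If the episode later passes 14 days, the text does not say whether it counts as a cycle 2 DLT. With discretionary counts and none near day 22, the onset date itself may be unknown.

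This limb matters because lenalidomide is the drug escalated across levels 1 to 4, and the Background gives hematologic toxicity as its main toxicity. The DLT count sets the MTD, which is the phase I primary goal and the dose for up to 31 further evaluable patients in phase II (16.12).

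The anemia limb is a separate and smaller problem: on the protocol's general hematologic scale it can hardly ever be met.

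**Working it through.** **1. The plan's own figure.** Section 16.227 tabulates the probability of escalating past a level with true DLT rate p:

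P = (1−p)³ + 3p(1−p)² × (1−p)³

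For p = 0.30: 0.343 + 0.441 × 0.343 = 0.494, against 0.49 stated. For p = 0.10, 0.20, 0.40 and 0.50 the formula gives 0.906, 0.709, 0.309 and 0.172, against 0.91, 0.71, 0.31 and 0.17. The table is right, provided every DLT is known when the cohort decision is made.

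**2. Can the ANC limb be met by day 28?** For onset on cycle 2 day d, the days available to day 28 are 29 − d (counting both ends) or 28 − d (elapsed). The first day on which the episode exceeds 14 days is d + 14 or d + 15.

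| Onset day | Days by day 28 (inclusive / elapsed) | Exceeds 14 days on day |
|---|---|---|
| 13 | 16 / 15 | 27–28 |
| 14 | 15 / 14 | 28–29 |
| 15 | 14 / 13 | 29–30 |
| 21 | 8 / 7 | 35–36 |
| 28 | 1 / 0 | 42–43 |

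From day 15 the limb cannot be met by day 28 on either count. On the elapsed count the boundary is day 14.

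**3. Effect on the cohort rule (16.222–16.224).** One episode confirmed late changes 0/3 to 1/3, so the cohort is expanded instead of escalated. Or it changes 1/6 to 2/6, so the MTD has been exceeded.

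**4. Exposure of the next cohort.** Cycle 1 is lenalidomide alone for 28 days (7.1). A new patient starting on day 29 reaches the combination on day 29 + 28 = 57. The latest decision falls on day 42–43, which is 57 − 43 = 14 to 57 − 42 = 15 days earlier. By then that patient has taken at most 14–15 of 21 lenalidomide doses at the next level, or 7–8 if onset was on day 21. The top level is 20 mg, below the 25 mg of the investigators' earlier study (Background). Assuming steady accrual of 10–15 patients a year (16.13), the number starting in that window is 10 × 14/365 = 0.4 to 15 × 15/365 = 0.6; it is up to 3 if patients are queued.

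**5. Grade 4 on Appendix V.** Grade 4 is a fall of at least 75% from the pretreatment value, so the threshold is 0.25 × baseline.

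- Hemoglobin: 12 → 3.0, 10 → 2.5, 8 → 2.0 g/dL. There is no absolute floor.
- Platelets: 200 → 50 × 10⁹/L is already grade 4, although 8.2 lets a new lenalidomide cycle start at 25,000/µL. Below 20 × 10⁹/L is also grade 4, unless the pretreatment count was already that low.

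So the scale makes the anemia limb very hard to reach and the platelet limb comparatively easy from a normal baseline.

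**The case against.** **The neutropenia text has a sensible reading.** An event that occurs in cycle 2 can be taken to mean onset in cycle 2, with the duration completed later. Section 8.2 requires an ANC of at least 1,000/µL to start a new cycle, so a patient at or below 500/µL on day 28 does not start cycle 3 and is evaluated weekly. Section 16.221 sets a minimum, and 16.223–16.224 fix no data cut at day 28. Sites must also call the Registration Office for a dose level and an open place before approaching each phase I patient (3.0, 6.1).

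This shows that a careful team could wait. It does not show that they must. Section 8.2 governs only that patient's next cycle. The duty in 7.213 to contact the Study Chair begins once a DLT exists, and an unresolved episode is not yet one. The Registration Office check carries no instruction to hold.

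**The scale is mostly settled.** A reader might infer that the protocol has no scale for hematologic DLTs. The documents do not support that: Appendix V is stated generally, 16.231 and 16.232 repeat it for phase I, and the CTCAE anemia grade is kept for reporting. The silence is in 7.221 alone. What stands is that the default scale leaves the anemia limb practically inert. It is also fair that the documents do not define CTCAE grade 4 anemia, so they cannot show how that grade would perform.

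**Blood counts.** A reader might infer from the 8.2 note suspending dose modifications in phase I that weekly counts stop for a neutropenic patient. That is strained, since the note concerns dosing. The gap rests on footnote 6 of the Test Schedule.

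**Conclusion.** The neutropenia point holds. As written, an ANC ≤0.5 × 10⁹/L episode starting on day 15 or later of cycle 2 (day 14 on an elapsed count) is not a DLT at day 28, the next cohort may start, and no rule holds the decision or says how later confirmation counts. The duration may also go unmeasured. The anemia point holds as a secondary one.

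The stakes are modest. Two stronger conclusions a reader might draw are not supported:

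- That patients would receive the combination at too high a level before the episode is decided. The 28-day lenalidomide-only cycle rules this out even in the latest case, by 14–15 days. What remains is some lenalidomide at the next level and an unclear DLT count.
- That the probabilities in 16.227 are biased by a known amount or in a known direction. The documents give no share of DLTs that would be late-onset neutropenia, and Appendix V works in opposite ways for hemoglobin and platelets.

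Febrile neutropenia, the platelet limbs and early-onset neutropenia still work. The change is worth making because it is cheap and the MTD depends on this count.

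**What to change.** **In 7.212:** state that an ANC ≤0.5 × 10⁹/L episode starting in cycle 2 is followed past day 28, counts as a cycle 2 DLT if it exceeds 14 days, and holds the cohort decision until it resolves or exceeds 14 days.

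**In the Test Schedule:** require blood counts at about days 8, 15 and 22 of cycle 2 for phase I patients.

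**In 7.221:** name the platelet scale. For anemia, use the CTCAE v4.0 grade already recorded under 10.6, or write an explicit absolute or transfusion-based criterion.

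**Cost.** The hold is at most 14–15 days (day 28 to day 42–43). For a cohort of three, accrual at 10–15 a year takes 73–110 days; adding 56 days of treatment gives 129–166 of the roughly 183 days that 16.13 allows, leaving about 17–54. The counts number at most 3 × 26 = 78. Research blood is already drawn on days 8 and 15, and weekly clinical examinations are already planned, so only day 22 adds a draw: at most 26. A few more DLTs may be counted.

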8.0 Dosage Modification Based on Adverse Events

8.1 Dose Levels (Based on Adverse Events in Tables 8.2 and 8.3)

* Dose level 1 refers to the starting dose.

Omit = The current dose(s) for the specified drug(s) during a cycle is skipped. The patient does not make up the omitted dose(s) at a later time

Hold/Delay = The current dose(s) of all drugs during a cycle is delayed. The patient does make up the delayed dose(s) when the patient meets the protocol criteria to restart drugs.

Discontinue = The specified drug(s) are totally stopped.

8.2 Lenalidomide

A new course of treatment may begin on the scheduled Day 1 of a new cycle if:

- The ANC is $\geq 1,000/\mu$ L;
- The platelet count is $\geq 25,000/\mu$ L;
- Any lenalidomide-related allergic reaction/hypersensitivity or sinus bradycardia/ other cardiac arrhythmia adverse event that may have occurred has resolved to ≤ grade 1 severity;
- Any other lenalidomide-related adverse event that may have occurred has resolved to \leq grade 2 severity.

If these conditions are not met on Day 1 of a new cycle, the subject will be evaluated weekly and a new cycle of lenalidomide will not be initiated until the toxicity has resolved as described above. If lenalidomide dosing was omitted during the previous cycle and was restarted with a one-level dose reduction without requiring an interruption for the remainder of the cycle, then that reduced dose level will be initiated on Day 1 of the new cycle. If lenalidomide dosing was omitted for the remainder of the previous cycle or if the new cycle is delayed due to toxicity newly encountered on the scheduled Day 1, then the new cycle will be started with a one-level dose reduction.

If either drug is discontinued, patient will come off treatment and go to event monitoring.

| → → Use the NCI Common Terminology Criteria for Adverse Events (CTCAE) version 4.0 unless otherwise specified $\leftarrow \leftarrow$ | | | | |
|---|---|--------------|---|--|
| CTCAE System/Organ/Class (SOC) | ADVERSE EVENT | AGENT | ACTION | |
| | BASED ON INTERVAL | ADVERSE E | EVENTS (Days 2-28) | |
| Investigations | Platelet count decreased*: (Platelets < 10,000/mm ³) | | Omit dose. Follow CBC weekly. If thrombocytopenia resolves to ≤ grade 3 restart lenalidomide at the same dose level. | |
| | | | If thrombocytopenia < 10,000/mm³ recurs, reduce dose by one dose level (5 mg) and continue therapy when platelet count ≥ 25,000/mm³. | |
| | Grade 4 Neutrophil count | | • Omit dose. | |
| | decreased* | | • Follow CBC weekly. | |
| | | Lenalidomide | If neutropenia has resolved to ≤ grade 2, resume dose at same level with GCSF support. | |
| Blood and lymphatic | ≥ Grade 3 Febrile | omi | Omit dose. | |
| system disorders | neutropenia | de | • Follow CBC weekly. | |
| | | | If neutropenia has resolved to ≤ grade 2, resume dose at same level with GCSF support. | |
| Cardiac Disorders | Sinus bradycardia/ other cardiac Arrhythmia Grade 2 | | Omit dose. Follow at least weekly. If the toxicity resolves to ≤ grade 1, reduce dose by one dose level (5mg) and continue therapy. | |
| | \geq Grade 3 | | • Discontinue study treatment and go to | |
| Vascular disorders | thromboembolic event \geq Grade 3 | | event monitoring. Omit dose and start anticoagulation; restart at investigator's discretion (maintain dose level). | |

| \rightarrow \rightarrow Use the NCI Common Terminology Criteria for Adverse Events (CTCAE) version 4.0 unless | | | |
|---|--|--------------------------|--|
| | otherwise | e specified \leftarrow | F |
| CTCAE System/Organ/Class (SOC) | ADVERSE EVENT | AGENT | ACTION |
| | BASED ON INTERVAL | ADVERSE E | VENTS (Days 2-28) |
| Immune system disorders | Allergic reaction Grade 2-3 | | Omit dose. Follow at least weekly. If the toxicity resolves to ≤ grade 1, reduce dose by 5 mg and continue therapy. |
| Anaphylaxis Grade 4 | | | • Discontinue study treatment and go to event monitoring. |
| | Erythema multiforme ≥ Grade 3 | Г | • Discontinue study treatment and go to event monitoring. |
| Skin and | Skin ulceration \geq Grade 2 | Lenalidomide | • Discontinue study treatment and go to event monitoring. |
| subcutaneous tissue disorders | Other: Non-blistering rash Grade 3 | | If Grade 3 omit dose. Follow weekly. If the toxicity resolves to ≤ grade 2 continue therapy. |
| | Other: Non-blistering rash Grade 4 | | • Discontinue study treatment and go to event monitoring. |
| Other | Non-hematologic toxicity assessed as lenalidomide related ≥ Grade 3 | | Omit dose. Follow at least weekly. If the toxicity resolves to ≤ grade 2, implement one dose reduction step and continue therapy. |

* use IWCLL/Hallek, December 2008 criteria (see Appendix V)

NOTE: Subjects who cannot tolerate the minimum dose 5 mg daily on days 1 - 21 of a 28 day cycle, are to be discontinued from the treatment phase of the study and go to event monitoring.

Note: Dose modification schedule as outlined in the table above will be applicable to all patients enrolled on the study. This schedule will not be applicable to patients during the two cycles of the combination therapy of the patients enrolled on the phase I portion of the study to clearly define MTD. Once patients on the phase I portion of the study have completed cycle #2 (1st combination cycle) they may be managed based on the dose modification criteria outlined in the table above. Dose modification due to toxicity will be based on dose de-escalation in 5 mg increments from the maximum dose obtained for the individual patient. The optimum dose in any individual patient may be determined by the investigator based on managing toxicity and maximizing response. The maximum dose of lenalidomide permitted will not exceed the MTD determined in the phase I portion of the study and is not to exceed 20 mg daily on days 1 - 21 of a 28 day cycle and the minimum dose permitted is 5 mg daily on days 1 - 21 of a 28 day cycle.

Dose re-escalation: For patients who are dose reduced either for disease or drug related toxicities, lenalidomide dose re-escalation can be considered provided all toxicity has resolved to \leq Grade 1. Patients can be started at minimum of 5mg PO daily on days 1 - 21 of a 28 day cycle and the dose titrated up at 5mg increments weekly to the target dose not to exceed the MTD determined in the phase I portion of the study. The rate of escalation is at the PI discretion based on patient tolerability and concern for tumor lysis syndrome.

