3.0 Patient Eligibility

Phase I only: Prior to discussing protocol entry with the patient, call the MCCC Registration Office () for dose level and to insure that a place on the protocol is open to the patient.

- 3.1 Inclusion Criteria
 - 3.11 Understand and voluntarily sign an informed consent form.
 - 3.12 Age \geq 18 years.
 - 3.13 Able to adhere to the study visit schedule and other protocol requirements.
 - 3.14 Diagnosis of B-CLL, confirmed by flow cytometric analysis and as per the criteria outlined by the IWCLL/Hallek December 2008. (Refer to Appendix III).
 - 3.15 Any prior therapy for B-CLL must have been discontinued \geq 28 days prior to registration.
 - 3.16 Patients must have an absolute lymphocyte count (ALC) of more than 5,000 cell/mm³.
 - 3.17 During Phase I: All patients with relapsed disease will be eligible if they have received at least 1 prior standard CLL therapy^{*} and no more than 4 prior therapies (one of which must be a purine analog and/or an alkylating agent).

During Phase II: All patients with relapsed disease will be eligible if they have received a minimum of 1 prior standard therapy^{*} and a maximum of 2 prior treatments (one of which must be a purine analog and/or an alkylating agent) for B-CLL and have developed relapse disease.

Note: Patients who have refractory disease (defined as – progressive disease on last treatment, or less than 6 months of clinical response to the last treatment) will not be eligible.

* Standard Therapies are defined as those listed in the NCCN guidelines for treatment of CLL.

- 3.18 ECOG performance status of 0, 1 or 2 at registration (see Appendix I).
- 3.19a The following laboratory values obtained \leq 14 days prior to registration:
 - Absolute neutrophil count $\geq 1500/\text{mm}^3$
 - Platelet count \geq 30,000/mm³
 - Serum creatinine $\leq 1.5 \text{ x ULN}$.
 - Total bilirubin $\leq 1.5 \text{ mg/dL}$ or direct bilirubin $\leq 1.0 \text{ mg/dL}$ for patients with Gilbert's syndrome
 - SGOT (AST) and SGPT (ALT) ≤ 2 x ULN or ≤ 5 x ULN if hepatic disease is present.

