Appendix II

Rai Staging System for CLL

| Modified 3-stage System | Rai Stage | Clinical Features |
|-------------------------|-----------|---|
| Low Risk | 0 | Lymphocytes (L) in blood |
| | | $> 5000/\text{mm}^3$ and marrow $> 30\%$ only |
| Intermediate Risk | Ι | L+ enlarged lymph nodes (LN) |
| | II | L + spleen and/or liver (LN + or -) |
| High Risk | III | L + anemia (Hbg < 11 gm/dl) |
| | IV | L + Thrombocytopenia < 100,000/µl. |

Subjects in the intermediate risk group must have evidence of active disease as demonstrated by at least one of the following criteria:

Massive or progressive splenomegaly and/or lymphadenopathy; (Massive splenomegaly is here defined by spleen tip > 6 cm below costal margin.)

Presence of weight loss > 10% over the preceding 6 month period;

Grade 2 or 3 fatigue;

Fevers $> 100.5^{\circ}$ F or night sweats for greater than 2 weeks without evidence of infection;

Progressive lymphocytosis with an increase of > 50% over a 2 month period or an anticipated doubling time of less than 6 months;

Worsening anemia or thrombocytopenia.

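### For baseline platelets below about 100,000/mm³, section 8.2 allows a full-dose lenalidomide restart at a lower count than it requires for a reduced-dose restart

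*Combined protocol and SAP*

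**What the plan says.** The lenalidomide table in section 8.2 omits the drug when platelets fall below 10,000/mm³ between Days 2 and 28, with weekly blood counts afterwards. Two restart rules follow in the same row.

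- First episode: "If thrombocytopenia resolves to ≤ grade 3 restart lenalidomide at the same dose level".
- Recurrence: "reduce dose by one dose level (5 mg) and continue therapy when platelet count ≥ 25,000/mm³".

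A third rule, above the table, governs Day 1 of a new cycle. It requires at least 25,000/µL; otherwise "a new cycle of lenalidomide will not be initiated until the toxicity has resolved as described above". A further rule starts the next cycle one level lower in this case, among others: "If lenalidomide dosing was omitted for the remainder of the previous cycle".

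The table's default scale is CTCAE v4.0 unless otherwise specified. The platelet row carries an asterisk, and the footnote reads "use IWCLL/Hallek, December 2008 criteria (see Appendix V". Appendix V grades platelets by percentage fall from pretreatment: 50%-74% is grade 3, and 75% or more is grade 4. It adds a rule for counts below 20,000 at any percentage fall: "this will be considered grade 4 toxicity, unless a severe or life-threatening decrease in the initial platelet count".

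Section 3.19a admits patients with platelets of 30,000/mm³ or more, and Appendix II defines Rai stage IV as "L + Thrombocytopenia < 100,000".

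**The concern.** Two of the three platelet rules use a fixed count, and they use the same one, 25,000. The first-episode rule uses a grade that depends on the patient's own baseline. For a low baseline, that grade can be met below 25,000.

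The order of the two restarts is then wrong. A patient recovering from a first fall below 10,000 may resume full dose at a count too low for a patient recovering from a second fall to resume one level lower. One would expect the larger dose to need at least as much recovery. The documents give no reason for the reverse.

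What is at stake is bleeding safety in the patients with the least platelet reserve. These patients are expected: the entry limit is 30,000, Rai stage IV lies below 100,000, and Appendix IV counts new or worsening thrombocytopenia below 100 x 10⁹ as a reason to treat.

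**Working it through.** **Inputs.** Trigger below 10,000; first-episode restart at grade 3 or less; recurrence and Day 1 at 25,000 (all section 8.2). Grade 4 at a fall of 75% or more, or a count below 20,000 (Appendix V). Lowest eligible baseline 30,000 (section 3.19a). The plan states no restart count for the first episode, so there is no figure to reproduce.

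**Formula.** With baseline B and count C, grade 3 or less requires C ≥ 20,000 and (B − C)/B < 75%, that is, C > 0.25 × B. The first-episode restart count is the larger of 20,000 and just above 0.25 × B.

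**Crossovers.** 0.25 × 80,000 = 20,000, so below a baseline of 80,000 the 20,000 limit decides. 0.25 × 100,000 = 25,000, so the gap closes at 100,000.

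| Baseline | First-episode restart, full dose | Recurrence restart, one level lower | Counts allowed below 25,000 |
|---|---|---|---|
| 30,000 to just under 80,000 | 20,000 | 25,000 | 20,000-24,999 |
| 90,000 | above 22,500 | 25,000 | 22,501-24,999 |
| 96,000 | above 24,000 | 25,000 | 24,001-24,999 |
| 100,000 | above 25,000 | 25,000 | none |
| 200,000 | above 50,000 | 25,000 | none |

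**Example.** Baseline 60,000, count 22,000 after a first fall below 10,000. The fall from baseline is 1 − 22/60 = 63%, which is grade 3, so full dose may resume. After a second fall, the same patient at 22,000 may not resume even one level lower.

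**When the rule can act.** Lenalidomide is given on days 1-21. With weekly checks, a fall found on day 15 is next checked on day 22, after the last dose, so no mid-cycle restart is possible under any threshold. A fall found on days 22-28 leaves no dose to omit, and the next decision is Day 1 at 25,000. The gap therefore matters for falls found by about day 14.

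**Dose at stake on one assumed path.** Dose 20 mg, baseline 60,000, fall found on day 8, count 22,000 on day 15 and at least 25,000 by the next Day 1. Planned over two cycles: 42 × 20 = 840 mg.

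- Current rule, restart on day 15: 14 × 20 + 21 × 20 = 700 mg.
- With a 25,000 floor, no restart, next cycle one level lower: 7 × 20 + 21 × 15 = 455 mg.
- Difference: 245 mg, made up of 7 × 20 = 140 from doses not resumed and 21 × 5 = 105 from the reduction.

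This shows what the floor could cost one patient at the top dose. It is not an expected value.

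**The case against.** The strongest reply is that 25,000 on Day 1 and the mid-cycle rules answer different questions. Day 1 commits the patient to a new 21-dose course. Within a cycle, 8.2 stops lenalidomide for platelets only below 10,000, so a patient who drifts to 22,000 without having fallen below 10,000 stays on full dose. A restart at 20,000 is already twice the stop limit. This stands, and it weakens the Day 1 comparison: a reader might infer that 8.2 treats 22,000 as unsafe for any dosing, and it does not. It does not answer the comparison within the row, where both rules concern mid-cycle restart after a fall below 10,000 and the larger dose has the lower limit. To that the only reply is that the window is narrow, which is true.

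A reader might also infer a fault at the high end, because above 100,000 the first episode needs a higher count than a recurrence (above 50,000 against 25,000 at a baseline of 200,000). The documents do not support that. The first-episode restart is at full dose and the recurrence restart is one level lower, so asking for more recovery before full dose is coherent.

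Finally, CTCAE might be thought to govern. The asterisk points to Appendix V. The CTCAE cut-points are not in the documents, so the gap cannot be sized on that reading.

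**Conclusion.** The point holds for baselines below about 100,000/mm³ and there only. On Appendix V grading, a full-dose restart after a first fall below 10,000 is allowed up to 5,000/mm³ below the count required for a reduced-dose restart after a recurrence. It is an inconsistency between thresholds, not a direct contradiction, and it is minor.

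Reach is small. It covers only patients found below 10,000 mid-cycle with doses still to come. Under section 4.0, footnote 6, the day 8 and day 15 counts in cycles 1 and 2 are at the physician's discretion, and later cycles schedule a count only before each cycle. Phase I patients are outside the schedule until cycle 2 is complete, and the investigator may adjust an individual's dose. The documents give no frequency for such falls.

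The conclusion assumes that the asterisk makes Appendix V the scale for this row and that any fall short of 75% counts as grade 3 or less. One matter stays open: Appendix V exempts patients with a severe initial decrease, so someone entering near 30,000 may have no platelet grade to apply. Nothing here touches alpha, power or the definition of dose-limiting toxicity.

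**What to change.** In the first-episode line of the 8.2 platelet row, keep the grade condition and add a count: thrombocytopenia grade 3 or less **and** platelets at least 25,000/mm³. This is one line, using a number that 8.2 already contains twice. It also gives a usable limit where no Appendix V grade applies.

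Do not replace the grade by 25,000 alone. At a baseline of 200,000 that would lower the full-dose restart from above 50,000 to 25,000, after a fall of more than 95% (1 − 10/200), and section 9.8 sets no platelet limit for the aspirin option.

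The cost falls on a few low-baseline patients at 20,000-24,999. They wait longer, and if no dose is resumed before day 21 they meet the general one-level reduction. At 5 mg there is no lower lenalidomide level, and the note under the table takes patients who cannot tolerate 5 mg off treatment, so the team should say how the general reduction applies there. Mid-cycle dosing at 10,000-24,999 without an earlier fall is left as it is. Sample size and the decision rules do not change.
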